6.9 Scheduled follow-up visits

After receiving randomization notice via the randomization CRF, Medtronic will provide the target dates and windows for each follow-up visit to the implanting center via the randomization CRF. Follow-up visit windows open on the Window Start date and remain open as defined below. It is recommended that subjects are scheduled as close as possible to the target date for a given follow-up visit.

Should a subject visit fall outside the pre-specified window, a Study Deviation must be reported and the original follow-up schedule maintained for subsequent visits. Data analyses include follow-up visits, regardless of whether the visit occurs within the window. Therefore, an early or late visit is preferred over a missed visit, but still must be accompanied by a deviation. Follow-up visit windows are listed in Table 7 and are based on days post-randomization.

Required visits post-randomization include follow-up visits at 3 months, 6 months, and every 6 months thereafter until study closure. During these visits information will be collected about adverse events (AE), health care utilization (HCU), Cardiovascular (CV) medications, and Heart Failure (HF) assessment, as well as additional information and procedures which vary by visit (see Table 5). Quality of Life (QoL) and Health outcome will be addressed using the KCCQ and the EQ-5D questionnaires, which subjects will complete during applicable study visits. Full device interrogation (interrogate ALL) data will be collected for subjects at the end of the visit (final interrogation) and a copy of the interrogation files (Save-to-Disk, S2D) must be sent to Medtronic, with a copy also being maintained at the center in the subject's file.

Figure 1: Visit Timeline

[figure not shown]

Table 7 Post-randomization follow-up windows

Study Follow-up Visit	Window (Calculated days post-randomization)		
	Window Start (days post-randomization)	Target (days post-randomization)	Window End (days post-randomization)
3 Month follow-up	56	91	105
6 Month follow-up	153	183	213
12 Month follow-up	335	365	395
18 Month follow-up	518	548	578
24 Month follow-up	700	730	760
30 Month follow-up	883	913	943
36 Month follow-up	1066	1096	1126
42 Month follow-up	1249	1279	1309
48 Month follow-up	1431	1461	1491
54 Month follow-up	1614	1644	1674
60 Month follow-up	1796	1826	1856
66 Month follow-up	1979	2009	2039
72 Month follow-up	2162	2192	2222
78 Month follow-up	2344	2374	2404
84 Month follow-up	2527	2557	2587
90 Month follow-up	2709	2739	2769

6.9.1 3 and 6 month Follow-up visits

- NYHA HF assessment
- Physical examination
- Blood measurements (if collected per standard of care)
- Current CV medications
- Current heart failure symptoms status
- Final device interrogation (Interrogate All)
- AV/VV optimization method (control group only, if optimization occurs per standard of care)
- Quality of Life and Health Outcome Measures:
 - Kansas City Cardiomyopathy Questionnaire (KCCQ)
 - EQ-5D
- Patient Global Assessment
- Report AEs, System Modifications, Study Deviations, Crossovers, and Healthcare Utilizations (as they occur)

6.9.2 12, 18, 24 month Follow-up visits

- NYHA HF assessment
- Physical examination
- Blood measurements (if collected per standard of care)
- Current CV medications
- Current heart failure symptoms status
- Final device interrogation (Interrogate All)
- AV/VV optimization method (control group only, if optimization occurs per standard of care)
- Quality of Life and Health Outcome Measures
 - Kansas City Cardiomyopathy Questionnaire (KCCQ)
 - EQ-5D
- Report AEs, System Modifications, Study Deviations, Crossovers, and Healthcare Utilizations (as they occur)

6.9.3 Follow-up visit every 6 months until study closure

- NYHA HF assessment
- Physical examination
- Blood measurements (if collected per standard of care)
- Current CV medications
- Current heart failure symptoms status
- Final device interrogation (Interrogate All)

- AV/VV optimization method (control group only, if optimization occurs per standard of care)
- Report AEs, System Modifications, Study Deviations, Crossovers, and Healthcare Utilizations (as they occur)

6.10 Device Interrogation (Interrogate All)

For the implant, randomization and follow-up visits, a final full “Interrogate ALL” device interrogation file (.pdd) must be obtained and saved in a digital format (e.g., USB). Store one copy at the site and send a copy to Medtronic. It is recommended that data are not cleared during any interrogation.

6.11 Adverse Events

The primary objective depends on complete reporting of HF events, including interventions for heart failure decompensation and cardiovascular adverse events (AEs). These are reported upon center awareness and assessed at scheduled follow-up visits to ensure all applicable hospitalizations and AE’s have been reported. Refer to section 8 for adverse events details.

6.12 Healthcare Utilization

Healthcare Utilization (HCU) information should be reported upon center awareness and assessed at all follow-up visits to ensure all applicable Healthcare Utilizations have been reported. All hospitalizations, emergency department visits, outpatient treatment involving overnight stay, cardiovascular-related urgent care and cardiovascular-related clinic visits will be considered reportable Healthcare Utilizations for this study. Any visit where changes occur to protocol-required programming parameters will be considered cardiovascular-related. For HCU’s involving changes to protocol-required programming parameters, both an initial and final device interrogation will be required, and a copy of the interrogation files must be sent to Medtronic with a copy also being maintained at the center in the subject’s file. Additionally, collection of current cardiovascular medications will be required for all HCU’s. Any remote transmissions via the Medtronic CareLink® system will also be collected.

Healthcare Utilization information will be included in the review of potential HF related events and hospitalizations by the blinded Endpoint Adjudication Committee (EAC). Supporting source documentation may be requested if needed for study or endpoint evaluation. Relevant documentation may include but is not limited to: a copy of the hospital discharge summary report, and medical records such as chest x-ray reports, echocardiogram reports, medication documentation, lab results related to the event and consultation reports (e.g., Heart Failure, Renal, Cardiology, Pulmonary, etc.).

6.13 System Modification

A system modification will be reported in the event the device and/or leads require invasive modification (e.g., device or lead explant, device or lead replacement, lead repositioning). In the event of a system modification, the follow-up schedule for the subject will remain unchanged. The following information is required to be collected for a system modification:

- Report reason for modification
- Report the details of the system modification procedure
- Device programming according to randomization assignment (aCRT ON for treatment group and aCRT OFF for control group)
- Device interrogation (initial and final “interrogate ALL”; a copy of the interrogation files must be sent to Medtronic with a copy also being maintained at the center)
- Report the associated AE

It is recommended that all explanted Medtronic products (device, leads, etc.) are returned to Medtronic for analysis when permissible by local laws and regulations.

In the event that a subject has a re-attempt after a previous unsuccessful system modification, the subsequent attempt(s) must be reported via CRF as separate system modifications.

6.14 Conditional Disengagement

After a patient is randomized every effort should be made to keep the subject in the study. However, it is recognized that there are circumstances where limited data may be collected, or study exit will need to occur. In these cases we will consider either modified data collection requirements where subjects may conditionally disengage in study procedures but data from the subject can still be collected because the subject has not revoked consent, or exit when study participation is completely ended. In randomized subjects, modified data collection is always preferred over exit.

Subjects may be conditionally disengaged from study procedures for any of the following reasons:

- Subject chooses to disengage (e.g., follow-up schedule cannot be adhered to, study burden too large, relocation to another geographic location but telephone follow-up still acceptable)
- Investigator deems conditional disengagement necessary (e.g. medically justified)

If the subject wishes to disengage from the study, or the investigator deems it necessary, the center is required to document the reason. Prior approval from the study team is required and a Limited Data Collection CRF needs to be completed. Data collection requirements no longer apply, but sites are encouraged to collect as much data as possible on the regular CRFs.

6.15 Study Exit

Subjects will be exited from the study for any of the following situations:

- Study completed
- Subject lost to follow-up
- Subject death
- Subject did not meet eligibility criteria and was not randomized
- Subject did not have a successful implant and no attempt at re-implant is made
- Subject did not provide consent or data protection authorization

- Subject chooses to exit (i.e. revokes consent)

Prior to exiting a subject from the study, it is recommended to follow the subject until all ongoing system- and procedure-related AEs are resolved or are unresolved with no further actions planned. After all study tests and procedures have been completed just prior to subject exit from the study, the subject may be informed of their randomization assignment. Following exit, subjects will continue to receive standard medical care. There will be no further required study-related follow-up visits for these subjects. All data available through the time of the subject's exit will be used for the study analyses. The following procedures are required to be collected at the exit visit:

- Report the reason for exit
- Vital status check
- Current CV medications
- Current heart failure symptoms status
- Initial and Final device interrogation, if available (Interrogate ALL)
- Report AEs, Study Deviations and Healthcare utilization (as they occur)

Subjects will not be replaced with newly enrolled subjects upon exit. As described in Section 11.3.4, the sample size accounts for attrition.

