6.15.2 Lost to follow-up

In the case that the subject is determined to be lost to follow-up, details of a minimum of two attempts to contact the subject, and the method of attempt (e.g., one letter and one phone record or two letters) must be recorded. In addition, regulations set forth by the governing Ethics Committee must be followed.

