11. STATISTICAL METHODS AND DATA ANALYSIS

11.1 General

Medtronic employed statisticians will perform the statistical analyses described in this section. Interim analyses will be performed by a Medtronic statistician other than the lead statistician for the study. The lead study statistician will be blinded to all interim analyses. All tests of treatment effects will be conducted in order to preserve an overall two-sided alpha level of 0.05 unless otherwise stated. An Intention-to-Treat analysis will be performed and will serve as the primary analysis for all objectives in this study. The Intention-to-Treat cohort will include all randomized subjects.

A Statistical Analysis Plan (SAP) will be created before the first interim analysis to specify analyses in further detail. In case the SAP deviates from this Clinical Investigation Plan (CIP), or the actual analysis deviates from CIP and/or SAP, this will be explained in the Final Report.

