11.2.2 Randomization

Patients will be randomized in a 1:1 ratio using permuted blocks with random block sizes. Randomization will be stratified by center and by NYHA class. Randomization schedules will be generated by a Medtronic statistician using computer-generated random numbers.

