11.3.4 Sample size rationale

A total of 1100 patients experiencing a primary endpoint will give 90% power to show a significant reduction of the incidence of the primary endpoint, accounting for 3 equally spaced interim analyses and assuming a true intent-to-treat hazard ratio of 0.82 for aCRT ON compared to aCRT OFF.

Version 1.0 of the CIP specified the total number of patients randomized as follows: With the inclusion of 2874 randomized patients enrolled over 3 years and followed for 2.3 more years, 1100 primary endpoint events are expected when the true control arm event-free rate is 75% at 2 years.

Version 2.0 of the CIP increases the total number of patients randomized to accommodate a lower event rate: With the inclusion of 3326 randomized patients enrolled over 4 years and followed for 3.5 more years, 1100 primary endpoint events are expected when the true control arm event-free rate is 85% at 2 years.

The study will randomize approximately 3500 patients in order to accommodate attrition due to early exit. The study will be event-driven and the DMC may advise to stop enrollment early when the primary endpoint rate is higher than expected.

Through simulation it was confirmed for version 1.0 of the CIP that the study will have 90% power under the following assumptions:

- 3000 patients randomized in 3 years with a uniform rate

[figure not shown]
- control arm event-free rate is 75% at 2 years
- LBBB is not confirmed by the ECG Core Laboratory in 10% of patients
- aCRT hazard ratio is 0.78 in confirmed LBBB patients, 1.0 in unconfirmed patients
- crossover rate is 5% at 2 years in aCRT arm and 8% at 2 years in control arm
- loss-to-follow-up rate is 5% at 2 years in both arms
- final analysis is done when 1100 events are accrued

For version 2.0 of the CIP, the simulation was updated and the power of 90% was confirmed with updated control group event rate expectation.

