4.3.3 Missing Data

Follow-up information for all participants is expected whether or not they continue with therapy or remain compliant (i.e. ITT principle). For survival analysis, if a subject is lost to follow up they will be censored at the last date for which the subject was known to be alive or free from the event. This means we assume non-informative censoring for lost to follow up. Here lost to follow up refers to conditional disengagement and early exit prior to study completion.

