4.4.1 Secondary Objective #1: All-cause mortality

The secondary objective #1 is to test the hypothesis that aCRT ON reduces all-cause mortality compared to aCRT OFF. All-cause mortality is one of the two components that comprise the primary endpoint.

Hypothesis

Let $S_T(t)$ and $S_C(t)$ denote the proportion of patients in the treatment arm (aCRT ON) and control arm (aCRT OFF), respectively, that have not died up to time t . Let $h_T(t)$ and $h_C(t)$ be the associated hazard functions. Under the Cox regression model that assumes proportional hazards, $h_T(t) = HR \cdot h_C(t)$, where HR is the hazard ratio of treatment compared to control. The null and alternative hypotheses are:

$$H_0 : HR = 1$$

$$H_A : HR \neq 1$$

Analysis Method

Similar to the primary endpoint, the hypothesis regarding the aCRT effect on all-cause mortality will be tested using a Cox proportional hazards regression model with a random site effect (frailty), stratified by NYHA class at enrollment. Section 4.3.2 has described this model in details. The analysis will be conducted using code similar to:

```
PROC PHREG DATA=mortality;  
  CLASS NYHA site;  
  MODEL time*death(0) = rand / TIES=efron;  
  STRATA NYHA;  
  RANDOM site/dist = gamma;  
RUN;
```

In these codes, death = 1 given an adjudicated death and death = 0 otherwise; time to death starts from the date of randomization and ends at the date of death for those who die, or the date of last documented follow-up since randomization for those who are censored. Date of last documented follow-up since randomization is the maximum value among the dates of randomization, randomization programming, any study scheduled follow-up visit, exit, adverse event onset, adverse event resolved, system modification, and healthcare utilization.

The model assumptions will be checked using the same methods that are described in detail in section 4.3.2 for the primary endpoint. That is, the assumption of proportional hazards between the treatment arms will be checked by testing the significance of treatment by time interaction term; and, the assumption of constant hazard ratio for treatment across NYHA classes will be checked by testing the significance of treatment by NYHA class interaction and evaluating the hazard ratio for treatment within each NYHA class.

Missing Data

Similar to the analysis for primary endpoint, we assume non-informative censoring for lost to follow up in the analysis of all-cause mortality.

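### The plan has no step at study closure to establish whether patients exited early have died, and it does not test its assumption that their censoring is non-informative

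*Protocol*

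**What the plan says.** - **Vital status at exit.** Protocol Table 5 marks the scheduled vital status item at Study Exit only. Section 6.15 lists loss to follow-up among the reasons for exit and requires a vital status check at exit, with no exception for lost patients. It does not say how the check is made.
- **Deaths before exit.** Table 5 also has a death row, completed as deaths occur. Section 8.3.1 requires a report once the investigator learns of a death.
- **Lost patients.** Section 6.15.2 asks the site to record "details of a minimum of two attempts to contact the subject, and the method of attempt"; two letters are given as an acceptable example.
- **After exit.** Section 6.15 requires no further study visits and adds: "All data available through the time of the subject's exit will be used for the study analyses".
- **At closure.** Section 6.15.1 calls for a Study Exit form with vital status for all subjects. The sentence stands under the heading for completed subjects and follows text on exiting subjects at closure.
- **Analysis.** SAP 4.3.3 censors lost patients and states: "This means we assume non-informative censoring for lost to follow up". SAP 4.4.1 repeats it for secondary objective #1: "we assume non-informative censoring for lost to follow up in the analysis of all-cause mortality". The two planned sensitivity analyses (SAP 4.3.4 and 4.4.1) concern core-laboratory LBBB confirmation and actual programming.

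**The concern.** All-cause death can often be established without any contact with the patient. The plan relies on a check at exit whose source is undefined for exactly those patients who do not respond, and it does not return to them at closure. A heart failure patient who stops responding may have died or become too ill, so non-informative censoring is least secure in this group. Nothing in the SAP would show whether the assumption fails.

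At stake is mainly secondary objective #1: deaths are undercounted and absolute mortality may be understated. The hazard ratio would be biased if loss were related to illness and differed by arm. Subjects are blinded but sites are not (protocol 5.6), so differential loss cannot be ruled out, although nothing in the documents shows it.

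The censoring date adds to the problem. SAP 4.3.2 and 4.4.1 count the exit date as documented follow-up. Protocol 11.3.3 censors early exits at the last documented visit, and SAP 4.3.3 at the last date known alive or event-free. A lost patient could therefore be counted alive up to an administrative exit date. SAP version 3.0 removed the conditional disengagement date for the reason that it is administrative and does not show patient contact.

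**Working it through.** **Inputs**
- Protocol 11.1: "preserve an overall two-sided alpha level of 0.05".
- Protocol 11.3.4: "A total of 1100 patients experiencing a primary endpoint will give 90% power", "assuming a true intent-to-treat hazard ratio of 0.82 for aCRT ON compared to aCRT OFF". The SAP 4.3.8 code uses 0.81818.
- Protocol 11.2.2: 1:1 allocation.
- Protocol 11.3.4, version 2.0: 3326 patients, accrual a = 4 years, further follow-up f = 3.5 years, control arm 85% event-free at 2 years, about 3500 to be randomised.
- Protocol 11.3.4, version 1.0 simulation: loss 5% at 2 years in both arms.
- Mortality: not given in either document. Assumed here at 2 to 6% per year.

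**Step 1. Reproduce the plan's figures.**
- Fixed design: 4(1.960 + 1.282)²/(ln 0.82)² gives 1068 events. With four-stage O'Brien-Fleming-type spending, stopping for efficacy or futility, and hazard ratio 0.81818, numerical integration gives about 1103. The stated 1100 is reproduced.
- With exponential times and uniform accrual, P = 1 − [exp(−λf) − exp(−λ(a+f))]/(λa). The hazards are −ln(0.85)/2 = 0.0813 (control) and 0.82 × 0.0813 = 0.0666 (aCRT). With 1663 patients per arm this gives about 1102 events without loss, so the version 2.0 expectation is reproduced too.

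**Step 2. Effect of loss on the primary endpoint.** The loss hazard is ν = −ln(0.95)/2 = 0.0256 per year. Let L = λ + ν. The probability of seeing a first event before loss is (λ/L){1 − [exp(−Lf) − exp(−L(a+f))]/(La)}. For 3500 patients:
- expected first events: 1159 without loss and 1084 with loss, so about 75 (6.5%) fall after loss;
- patients lost before any primary event: about 377 (10.8%).

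The 1084 is 16 short of 1100. The trial is event-driven, so this costs follow-up time rather than power, provided it runs to 1100.

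**Step 3. Deaths after loss.** Use the same formulas with mortality m in place of λ. For m = 4%, L = 0.0656:
- lost alive before closure: 3500 × (0.0256/0.0656) × 0.301 = 412;
- all deaths by closure: 3500 × 0.1966 = 688;
- deaths seen before loss: 642, so 46 are unseen.

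| Assumed mortality per year | Lost before closure | All deaths | Deaths after loss | Share of deaths |
|---|---|---|---|---|
| 2% | 434 (12.4%) | 364 | 25 | 6.9% |
| 4% | 412 (11.8%) | 688 | 46 | 6.7% |
| 6% | 391 (11.2%) | 978 | 64 | 6.6% |

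**Step 4. Precision.** Losing 6.7% of deaths widens the standard error of the log hazard ratio by 1/√(1 − 0.067) = 1.035, about 3.5%. Precision is a small part of the problem; the untested assumption matters more.

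**The case against.** The protocol does more than a quick reading suggests. Four stronger readings are tempting, and the documents support none of them.

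- **That vital status is recorded only at an exit visit, and is by definition unknown in lost patients.** Deaths are also reported as they occur, and 8.3.1 asks the centre to try to retrieve information on deaths at remote sites. The exit check applies to lost patients too, and a site could make it from its own records.
- **That two unanswered letters make a patient lost.** Section 6.15.2 sets a minimum for documentation once loss has been determined. Section 6.14 asks for every effort to keep randomised subjects and prefers limited data collection to exit.
- **That later checks are ruled out.** The gap is one of silence. The sentence in 6.15 does not forbid using a later death date, and 8.1.2 asks for continued follow-up of some exited subjects with unresolved system or procedure events. Case report forms, their instructions and the monitoring plan are separate documents that may say more.
- **That 390 to 430 patients will be exited as lost.** SAP 4.3.3 counts both conditional disengagement and early exit as loss. If the 5% has that meaning, it includes disengaged subjects who still supply data and subjects who revoked consent and may not be traceable.

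It is also fair that planning assumes equal loss in both arms and that subjects are blinded, so no mechanism for differential loss is shown.

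These points limit the size of the concern but do not close the gap. No text names a source for the exit check in a patient who cannot be reached, asks for a check on earlier exits at closure, or tests the censoring assumption. Leaving the matter to local practice across about 250 centres risks uneven ascertainment.

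**Conclusion.** The gap is real and of moderate importance. It mainly affects the completeness of all-cause mortality and the credibility of non-informative censoring. It should not be read as a loss of primary power.

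The illustrative size is 11 to 12% of 3500 patients lost, and 25 to 64 unseen deaths, about 7% of all deaths. This rests on four assumptions: the version 1.0 loss rate stays constant over 4 + 3.5 years; it covers only traceable losses; mortality is 2 to 6% per year; and lost patients die at the same rate as those followed. Within that mortality range the figures are an upper guide to what a check could recover. Higher mortality among lost patients would raise the number unseen, but the documents give no basis for a figure. Neither the existence nor the direction of bias in the hazard ratio can be established from the documents.

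**What to change.** - **Protocol 6.15, 6.15.2 and Table 5:** at study closure, sites obtain vital status and any date of death for every randomised subject exited early, from medical records, the treating physician or public registers, where consent and local law allow. Amend the sentence in 6.15 on data through exit so that these dates may be used.
- **SAP 4.4.1:** count the recovered deaths and extend follow-up to the confirmed vital-status date, for patients found alive as well as those found dead. Censor subjects whose status stays unknown at the last date known alive, not at an administrative exit date. Reconcile this with SAP 4.3.2 and 4.3.3 and protocol 11.3.3.
- **Primary composite:** use the recovered deaths only in a sensitivity analysis, because HF events are not observed after exit.

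The cost is a modest record check at sites, with no visit and no new staff, plus changes of wording in both documents. Coverage will be incomplete where consent has been revoked or local law does not permit the check.
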